Cohort 3	1800mg bid	1800mg bid	1800mg bid	1800mg tid	1800mg tid	1800mg tid

There will be 8 study visits (screening, baseline and month 1-6), all study visits after the baseline visit will be 28±7 days apart, followed by a 12 week observation period. At each visit, patients will have medical history, measurement of vital signs (blood pressure, heart rate, respiratory rate and temperature), review of concomitant medications, review of study drug diary, recording of adverse events, BCVA, eye examination, and anterior chamber tap. MP1 microperimetry will be done at screening and baseline visit. Optical Coherence tomography will be done at the screening and baseline visit and repeated every 3 months. MAIA microperimetry will be done at screening and baseline visit and repeated every month. Fundus autofluorescence and Ultrawide field fundus photographs will be obtained at screening and month 6 visit. At all visits where needed, microperimetry will be performed first followed by OCT, FAF and UWFP. Serum levels of NAC pre- and post-dose will be measured at baseline, week 12 and 24. When all 10 subjects in cohort 1 have had a week 4 visit, the PI will review safety and tolerability with study team members and if there has been good safety and tolerability, enrollment will begin for cohort 2. When all 10 subjects in cohort 2 have had a week 4 visit, the PI will

review safety and tolerability with study team members and if there has been good safety and tolerability, enrollment will begin for cohort 3.

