4.3 DOSING AND DOSE ESCALATION

This is a dose-escalation study in which 6 doses of NAC effervescent tablets are being tested: 600mg bid, 600mg tid, 1200mg bid, 1200mg tid, 1800mg bid and 1800mg tid. Patients will be given the dose pre-determined for the cohort they enter upon enrollment. The most common side effect of NAC is nausea and vomiting. If a patient cannot tolerate the assigned dose of NAC due to nausea and/or vomiting, the dose will be reduced to the dose immediately below the current dose. If that dose cannot be tolerated, the dose will be reduced to the next lowest level. This will be done until a tolerated dose is identified and the patient will be maintained on that dose throughout the trial. If a patient cannot tolerate the starting dose of 600mg bid, they will be reduced to 600mg qd. If a patient cannot tolerate a dose of 600mg qd, they will be exited from the trial. If 3 of the first 5 subjects in a cohort or a total of 5 subjects are unable to tolerate a particular dose of NAC, no additional subjects will be treated with that dose and the dose immediately below it will be designated the maximum tolerated dose. All subsequent subjects enrolled in the study will be treated with the maximum tolerated dose.

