5.3.2 Serious Adverse Events

An AE should be classified as **SERIOUS** if:

- It resulted in death (i.e., the AE caused or led to death).
- It was life threatening (i.e., the AE placed the subject at immediate risk of death; it does not apply to an AE that hypothetically might have caused death if it were more severe).
- It required or prolonged inpatient hospitalization (i.e., the AE required at least a 24-hour inpatient hospitalization or prolonged a hospitalization beyond the expected length of stay; hospitalizations for elective medical/surgical procedures, scheduled treatments, or routine check-ups are not SAEs by this criterion).
- It was disabling (i.e., the AE resulted in a substantial disruption of the subject’s ability to carry out normal life functions).
- It resulted in a congenital anomaly/birth defect (i.e., an adverse outcome in a child or fetus of a subject exposed to the molecule or study drug prior to conception or during pregnancy).
- It does not meet any of the above serious criteria but may jeopardize the subject or may require medical or surgical intervention to prevent one of the outcomes listed above.

Sight-threatening adverse events

An adverse event is considered to be sight-threatening if it meets one or more of the following criteria and will be reported as a serious adverse event (SAE):

- The event causes a decrease in visual acuity of greater >30 letters (compared with the last assessment of visual acuity prior to the most recent treatment) lasting >1 hour.

- The event causes a decrease in visual acuity to the level of light perception or worse lasting >1 hour.
- The event requires surgical intervention (e.g, conventional surgery, vitreous tap or biopsy with intravitreal injection of antibiotics, or laser or retinal cryopexy with gas) to prevent permanent loss of sight.
- The event is associated with severe intraocular inflammation (i.e., 4+ anterior chamber cell/flare or 4+ vitritis).
- In the opinion of the investigator, the event may require medical intervention to prevent permanent loss of sight.

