5.3.5 Plans to Decrease Potential Risks and Increase Safety

Detailed ocular examinations (e.g., VA, slit lamp examination and dilated fundus examination) will be performed every month. The Principal Investigator will review all adverse events. The appropriate IRB will be notified immediately of any serious adverse events and will be notified in yearly renewals of all other adverse events. The IRB and FDA will be notified of any interruption in enrollment or change in the conduct of the study. Study drug administration will be held for subjects who experience certain systemic or ocular adverse events related to the drug. In the event any subject develops an adverse event in the study eye that is considered by the designated evaluating physician to be severe in intensity, serious consideration should be given to withdrawing the subject from the study.

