Appendix A

Schedule of Activities for Subjects with RP											
Protocol Activities		BL	28 _± 7d	56 _± 7d	84 _± 7 d	112 _± 7d	140 _± 7d	168 _± 7d	196 _± 7d	224 _± 7d	252 _± 7d
	Screening	Day1	W4	W8	W12	W16	W20	W24	W28	W32	W36
Informed Consent	X										
Eligibility Criteria	X										
Demographics	X										
Medical History/ Concomitant Medications	X	X	X	X	X	X	X	X	X	X	X
Vital Signs	X	X	X	X	X	X	X	X	X	X	X
BCVA	X	X	X	X	X	X	X	X	X	X	X
Slit Lamp Examination	X	X	X	X	X	X	X	X	X	X	X
Funduscopy Examination	X	X	X	X	X	X	X	X	X	X	X
Paracentesis (study eye)	X	X	X	X	X	X	X	X	X	X	X
Blood Draw for RNA & DNA samples	X										
Blood Draw for serum bilirubin levels	X										
Blood Draw for measurement of oxidative markers	X	X	X	X	X	X	X	X	X	X	X
Blood Draw for measurement of plasma NAC levels (before administration of oral NAC and 1 & 2 hours after administration – 2 hour draw optional)		X			X			X			
MP1 microperimetry	X	X									

MAIA microperimetry	X	X	X	X	X	X	X	X	X	X	X
SD-OCT	X	X			X			X			X
Fundus autofluorescence	X							X			
Ultrawide angle fundus photo	X							X			
Treatment with NAC		X	X	X	X	X	X	X			
Adverse Events		X	X	X	X	X	X	X	X	X	X

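### The >30-letter sight-threatening SAE criterion has an undefined, moving comparator, so one event whose loss builds over two or more visits can miss it

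*Combined protocol and SAP*

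**What the plan says.** Under its sight-threatening heading, section 5.3.2 lists this trigger: "The event causes a decrease in visual acuity of greater >30 letters". The loss must persist for over an hour, and a bracketed clause sets the reference point: "compared with the last assessment of visual acuity prior to the most recent treatment". It is the only criterion that sets a number of letters lost. The other acuity criterion is absolute and needs no comparator: "The event causes a decrease in visual acuity to the level of light perception or worse lasting >1 hour". The section does not define treatment.

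Two things could be meant:

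- **The drug.** Section 4.3 lists the regimens as "600mg bid, 600mg tid, 1200mg bid, 1200mg tid, 1800mg bid and 1800mg tid". The Appendix A row "Treatment with NAC" is marked from Day 1 to Week 24.
- **The tap.** Appendix A schedules paracentesis of the study eye at Screening, Day 1 and each of the nine visits from Week 4 to Week 36, which makes 11 taps. Section 5.3.4 also times adverse-event follow-up from a procedure, not from dosing.

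BCVA is measured at every one of those visits. The study description says that "all study visits after the baseline visit will be 28±7 days apart". It describes the off-drug phase separately: "followed by a 12 week observation period". On acuity testing, section 5.3.5 adds: "Detailed ocular examinations (e.g., VA, slit lamp examination and dilated fundus examination) will be performed every month".

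**The concern.** A comparator placed before the latest treatment works when treatments are discrete and widely spaced, because it then marks the state of the eye before the intervention under suspicion. With a drug taken several times a day, the latest treatment is always hours old. The last acuity measured before it is simply the last acuity measured, and that may already include part of the loss being judged.

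What is at stake is classification and speed of reporting. Under section 5.3.3 an SAE reaches the principal investigator within 48 hours and the IRB within a week; sections 3.3 and 5.3.5 call for immediate IRB notice. Those two sections leave all other adverse events to the yearly renewal. An event that misses this trigger, and that no other criterion catches, could therefore be reported to the IRB yearly instead of promptly. Safety is the primary objective, and a complication of one of the 11 taps is a foreseeable use of the rule.

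**Working it through.** The plan gives no figure to reproduce here, so the check applies the rule as written to the visit schedule.

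**Inputs from the protocol.** The threshold is more than 30 letters (5.3.2). BCVA and a tap occur at every visit, Day 1 and Weeks 4 to 36 (Appendix A). NAC runs from Day 1 to Week 24 (Appendix A).

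**Assumptions.** One event begins after a stable acuity of V letters and costs 20 letters by the first measurement and 20 more by the second. BCVA on a visit day precedes that day's tap and clinic dose; the protocol does not state the order.

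**Formula.** Counted loss = comparator BCVA − current BCVA. The criterion is met if this exceeds 30.

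At the first measurement the counted loss is V − (V − 20) = 20 in every case, so the criterion is not met. At the second measurement acuity is V − 40:

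| Setting | Meaning of treatment | Comparator | Counted loss | Met? |
|---|---|---|---|---|
| Two scheduled visits on drug | NAC | V − 20 | 20 | No |
| Two scheduled visits on drug | Tap | V − 20 | 20 | No |
| Two unscheduled visits, no new tap, dosing continues | NAC | V − 20 | 20 | No |
| Same, but no dose after the first measurement | NAC | V | 40 | Yes |
| Two unscheduled visits, no new tap | Tap | V | 40 | Yes |
| Weeks 28 and 32, NAC ended at Week 24 | NAC | V (Week 24) | 40 | Yes |
| Weeks 28 and 32 | Tap | V − 20 | 20 | No |
| Any of the above, last BCVA before onset held fixed | Not needed | V | 40 | Yes |

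The same 40-letter event is therefore counted as 20 or 40 letters according to an undefined word and, on the NAC reading, according to whether dosing went on. Section 5.3.5 provides for holding the drug after certain related events, so the fourth row is a real possibility.

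**Range.** When the comparator moves at each visit, a two-step loss misses the criterion whenever neither step exceeds 30. The totals that can be missed run from 16 + 15 = 31 to 30 + 30 = 60 letters. Over three steps the upper limit is 3 × 30 = 90, if starting acuity allows.

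**Limits of the effect.** A loss of 31 letters within one interval meets the criterion at once on both readings. On the NAC reading the comparator stops moving when dosing ends. A steady 11 letters per visit then gives 3 × 11 = 33 letters between Week 24 and Week 36 and qualifies, while 10 per visit gives exactly 30 and does not. These rates illustrate how the rule behaves; the documents give no rate of acuity loss.

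**The case against.** The strongest reply is that the criterion asks what an event causes and is aimed at acute, attributable loss. A recent comparator is a sensible way to keep the slow progression of retinitis pigmentosa out of SAE reporting. This stands, and it is why a Day 1 comparator is not recommended as a trigger.

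A second reply is that a careful investigator would take the most recent treatment to be the one before the event began, and would count all 40 letters as the loss from one event. That is a reasonable intention to attribute to the rule, but the text does not state it. The fix would write it down.

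Third, the tap reading handles closely spaced unscheduled visits correctly, as the table shows. This also stands. The weakness on that reading is confined to loss spread across scheduled visits.

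Fourth, other routes to an SAE need no letter comparator: light perception or worse, need for surgery, severe intraocular inflammation, disability, jeopardy to the subject, and the investigator's opinion. They would catch many large losses, and severe inflammation is directly relevant to taps. They are partial backstops, because several rest on judgement and none counts letters lost.

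Finally, the primary outcome in section 3.2.1 is the incidence and severity of adverse events. A worsening is recorded and graded under sections 5.1 and 5.2 whether or not it is labelled serious. This stands too: the event is not lost from the data, and only its seriousness and speed of reporting are affected.

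**Conclusion.** The point holds as a defect of definition with a limited effect. During dosing, one event whose acuity loss builds over two or more visits can exceed 30 letters in total without meeting the only numeric acuity-loss criterion. Two-visit totals of 31 to 60 letters are exposed. The result rests on a literal reading of the comparator and on BCVA being measured at each visit; the 20-plus-20 pattern is an assumption.

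A reader might infer three stronger claims that the documents do not support:

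- **That a large cumulative loss can never qualify.** It can, if more than 30 letters go within one interval, or if they go between Week 24 and Week 36 on the NAC reading.
- **That SAE counts on and off drug will be compared on unequal terms.** Section 4.5.1 plans a summary of treatment-emergent events and separates only those recorded before NAC. It plans no on-drug versus off-drug contrast. On the tap reading, scheduled visits follow the same rule throughout.
- **That serious vision loss will be under-counted in this trial.** The documents give neither an expected rate of such events nor the share the other criteria would miss, so no size can be put on this.

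**What to change.** In section 5.3.2, keep the >30-letter threshold and replace the comparator with the last BCVA measured before onset of the event. Hold that value fixed for the duration of the event, and apply the rule identically on and off drug through Week 36. The criterion then no longer depends on what treatment means or on whether dosing continued.

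Cumulative change in BCVA from Day 1 can be summarised by visit alongside the safety data, without making it an SAE trigger. That keeps slow losses visible while sparing the SAE listing from natural progression.

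The cost is one sentence of protocol text and no new assessments, since Appendix A already has BCVA at every visit. An onset date is needed for each event, and section 5.1 already relies on onset when judging causality. Expect an occasional additional SAE report. In the other direction, after Week 24 on the NAC reading, unrelated earlier loss would no longer add to a later event. For example, 15 letters lost by Week 28 and then a 20-letter event now total 35 against Week 24, but would count as 20. That agrees with a criterion about what the event caused, and the Day 1 summary would still show the full 35.

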5.3.3 SAE Reporting

Sub-Investigators should report all SAEs to the PI within 48 hours of observing or learning of the event. For initial SAE reports, investigators should record all case details that can be gathered within 48 hours on the SAE page of the CRF. The PI will inform the IRB within 1 week of being informed of the SAE.

5.3.4 Type and Duration Of Follow-Up After Adverse Events

All reported AEs should be followed until resolution or until 1 month after the procedure. Subjects who have an ongoing study related SAE will be followed by the investigator or his or her designee until the event is resolved or determined to be irreversible, chronic, or stable by the investigator.

5.3.5 Plans to Decrease Potential Risks and Increase Safety

Detailed ocular examinations (e.g., VA, slit lamp examination and dilated fundus examination) will be performed every month. The Principal Investigator will review all adverse events. The appropriate IRB will be notified immediately of any serious adverse events and will be notified in yearly renewals of all other adverse events. The IRB and FDA will be notified of any interruption in enrollment or change in the conduct of the study. Study drug administration will be held for subjects who experience certain systemic or ocular adverse events related to the drug. In the event any subject develops an adverse event in the study eye that is considered by the designated evaluating physician to be severe in intensity, serious consideration should be given to withdrawing the subject from the study.

6. INVESTIGATOR REQUIREMENTS

6.1 STUDY INITIATION

Before the start of this study, the following documents must be on file at Johns Hopkins University or its appointed representative:

- Current curricula vitae of the Principal Investigator
- Written documentation of IRB approval of protocol (identified by Johns Hopkins University, protocol number or title and date of approval) and informed consent document (identified by Johns Hopkins University protocol number or title and date of approval)
- A copy of the IRB-approved informed consent document
- Written documentation of IRB review and approval of any advertising materials to be used for study recruitment, if applicable
- The informed consent document and any advertising materials must also be reviewed and approved by the Johns Hopkins University Legal Department.
- Certified translations of IRB approval letters, pertinent correspondence, and approved informed consent document (when applicable)

6.2 STUDY COMPLETION

The following data and materials are required by Johns Hopkins University before a study can be considered complete or terminated:

- Laboratory findings, clinical data, and all special test results from screening through the end of the study follow-up period (if applicable)
- Case Report Forms properly completed by appropriate study personnel and signed and dated by the investigator (if applicable)
- Copies of protocol amendments and IRB approval/notification (if applicable)

- A summary of the study prepared by the Principal Investigator (will accept IRB summary close letter) (if applicable)
- All regulatory documents (e.g., curricula vitae for each Principal Investigator)

6.3 INFORMED CONSENT

Informed consent documents will be provided to each subject.

The informed consent document must be signed and dated by the subject or the subject's legally authorized representative before his or her participation in the study. The case history for each subject shall document that informed consent was obtained prior to participation in the study. A copy of the informed consent document must be provided to the subject or the subject's legally authorized representative. If applicable, it will be provided in a certified translation of the local language.

Signed consent forms must remain in each subject's study file and must be available for verification at any time.

The following basic elements must be included:

A statement that the study involves research, an explanation of the purposes of the research and the expected duration of the patient's participation, a description of the procedures to be followed, and identification of any procedures or drug used for purposes which are experimental

- A description of any reasonably foreseeable risks or discomforts to the patients
- A description of any benefits to the patient or to others which may reasonably be expected from the research. A description that there may be no benefit from this research.
- A disclosure of appropriate alternative procedures or courses of treatment, if any, that might be advantageous to the patient
- A statement describing the extent, if any, to which confidentiality records identifying the patient will be maintained and that notes the possibility that the FDA and the Johns Hopkins University and the drug manufacturer may inspect the records

- For research involving more than minimal risk, an explanation as to whether any compensation and any medical treatments are available should injury occur and, if so, what they consist of or where further information may be obtained
- An explanation of whom to contact for answers to pertinent questions about the research and research patient's rights, and whom to contact in the event of a research-related injury to the patient
- A statement that participation is voluntary, that refusal to participate will involve no penalty or loss of benefits to which the patient is otherwise entitled, and that the patient may discontinue participation at any time without penalty or loss of benefits to which the patient is otherwise entitled

6.4 INSTITUTIONAL REVIEW BOARD OR ETHICS COMMITTEE APPROVAL

This protocol, the informed consent document, and relevant supporting information must be submitted to the IRB/EC for review and must be approved before the study is initiated. The study will be conducted in accordance with U.S. FDA, applicable national and local health authorities, and IRB/EC requirements.

The Principal Investigator is responsible for keeping the IRB/EC apprised of the progress of the study and of any changes made to the protocol as deemed appropriate, but in any case the IRB/EC must be updated at least once a year. The Principal Investigator must also keep the IRB/EC informed of any significant adverse events.

Investigators are required to promptly notify their respective IRB/EC of all adverse drug reactions that are both serious and unexpected. This generally refers to serious adverse events that are not already identified in the package insert and that are considered possibly or probably related to the study drug by the investigator. Some IRBs or ECs may have other specific adverse event requirements that investigators are expected to adhere to. Investigators must immediately forward to their IRB/EC any written safety report or update provided by Johns Hopkins University (e.g., IND safety report, Investigator Brochure, safety amendments and updates, etc.).

6.5 CASE REPORT FORMS

All CRFs should be filled out completely by appropriate personnel. The CRF should be reviewed, signed, and dated by the investigator.

All CRFs should be completed in a neat, legible manner to ensure accurate interpretation of data. Black ink is required to ensure clarity of reproduced CRF copies. When making changes or corrections, cross out the original entry with a single line, and initial and date the change. **DO NOT ERASE, OVERWRITE, OR USE CORRECTION FLUID ON THE ORIGINAL.**

6.6 STUDY DRUG ACCOUNTABILITY

The Investigator is responsible for the control and distribution of study drug.

All partially used or empty containers should be disposed of at the study site according to institutional standard operating procedure.

6.7 DISCLOSURE OF DATA

Subject medical information obtained by this study is confidential, and disclosure to third parties other than those noted below is prohibited.

Upon the subject's permission, medical information may be given to his or her personal physician or other appropriate medical personnel responsible for his or her welfare.

Data generated by this study must be available for inspection upon request by representatives of the U.S. FDA, national and local health authorities, the drug manufacturer and the IRB/EC for each study site, if appropriate.

